5. TREATMENT ALLOCATION AND BLINDING

5.1. Randomization

Central randomization will be implemented in this study. Patients will be randomized to 1 of 3 treatment arms, based on a computer-generated randomization schedule prepared by or under the supervision of the sponsor before the study. The randomization will be balanced by using permuted blocks. The Interactive Web Response System (IWRS) will assign a unique treatment code, which will dictate the treatment assignment and matching study drug kit for the patient.

Approximately 324 eligible patients will be randomized in a 2:1:1 ratio to the following groups:

- Placebo
- 5.0 mg MIN-117
- 2.5 mg MIN-117

The investigator will not be provided with randomization codes. The codes will be maintained within the IWRS, which has the functionality to allow the investigator to break the blind for an individual patient, if needed.

5.2. Blinding

Under normal circumstances, the blind should not be broken until all patients have completed the study and the database is locked. Otherwise, the blind should be broken only if specific emergency treatment/course of action would be dictated by knowing the treatment the patient is receiving. In such cases, the investigator may in an emergency determine the identity of the treatment by IWRS. Telephone contact with the sponsor or its designee will be available 24 hours per day, 7 days per week.

In the event the blind is broken, the sponsor must be informed as soon as possible. The date, time, and reason for the unblinding must be documented by the investigator in the appropriate section of the electronic case report form (eCRF), and in the source document. The documentation received from the IWRS indicating the code break must be retained with the patient's source documents in a secure manner (e.g., sealed envelope) so as not to unblind the treatment assignment to the study site, sponsor/contract research organization (CRO) personnel. The investigator is also advised not to reveal the study treatment assignment to the study site or sponsor personnel.

6. DOSAGE AND ADMINISTRATION

On Day 1 (Visit 2) of the double-blind treatment phase, patients will be randomized to receive placebo, 5.0 mg MIN-117, or 2.5 mg MIN-117, PO, once daily for 6 weeks (Table 1).

Study drugs will be packaged using a double-dummy, double-blind design. The study drugs will be packaged in individual patient kits containing 6 weekly blisters, with each blister containing medication sufficient for 8 days (1 week of treatment and 1 day of overage). Medications blisters will be dispensed to the patients at Visit 2 (3 blisters), Visit 3 (2 blisters), and Visit 4 (1 blister) to ensure intra-visit daily dosing, including the allowed visit windows (± 3 days), are covered. Daily dose will consist of 2 capsules containing the intended dose (MIN-117 or Placebo). MIN-117 capsules are available in 2.5 mg strength.

Table 1: Characteristics of the Treatment and Dosage

Treatment	Capsule Strength / Number		Total Number of Capsules	
	No. of MIN 2.5 mg capsules	No. of MIN-117 placebo capsules	During Study Participation	Total Capsules Dispensed
5.0 mg MIN-117	2	-	84	96
2.5 mg MIN-117	1	1	84	96
Placebo	-	2	84	96

Placebo and MIN-117 capsules are identically matched in appearance.

The study drug should be administered in a single dose in the morning at approximately the same time each day with or without food per patient's food intake habit. Capsules should be swallowed whole with water and not divided, crushed, chewed, or placed in water.

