- ^a Visits 3 to 6 may occur within a ± 3 -day window relative to Baseline (Visit 2). Visit 2 may occur within +7 day window relative to Visit 1 (i.e., the scening period may be extended to 28 days) upon Sponsor's decision.
- ^b Visit 5 represents the end-of-treatment or early withdrawal (EW) visit, and patients who discontinue the study prematurely should undergo all assessments indicated for this visit.
- ^c To participate in the optional pharmacogenomic component of this study, patients must sign the pharmacogenomic informed consent form, indicating their willingness to participate.
- ^d For all women of childbearing potential, serum pregnancy testing will be performed at Screening (Visit 1), Baseline (Visit 2), and post study visit (Visit 6). Urine pregnancy testing will be performed at Baseline (Visit 2), and Visits 4, 5, and 6.
- ^e After meeting eligibility criteria during their Screening visit, patients will taper off their current psychotropic medications. Patients will be free of any psychotropic medications for a period of 1 week (or 2 weeks for a MAO inhibitor, 4 weeks for fluoxetine) prior to randomization.
- ^f All procedures (except dispensing of study medication) should be completed on Day 1 before randomization.
- ^g Only drug administration at Visit 5.
- ^h Samples will be obtained within 1 hour prior to dosing, and approximately 2 to 4 hours after dosing (the approximate time of maximum plasma concentration for MIN-117) on Visits 2, 3, 4, and 5. Additionally, 1 sample will be taken on Visit 6.
- ⁱ A 10-mL blood sample will be collected only from patients who give informed consent for the pharmacogenomic component of this study. A sample collected at a later time point does not constitute a protocol violation and would not require protocol amendment.
- ^j Sleep recording by using Somno-Art for 1 night after Screening, 1 night before dosing, and 1 night after dosing on Visit 2 and Visit 5.
- ^k Triplicate ECGs to be performed at least 1 minute apart within 5 minutes, while the patient is supine for ≥ 10 minutes.
- ^l Patients will be weighed clothed (lightly) and without shoes.
- ^m Clinical laboratory tests will include hematology, serum chemistry (including serum lipid profile, and fasting blood glucose), and urinalysis. Patients must fast for 8 hours before the blood sample is taken.

ABBREVIATIONS

ADR	Adverse drug reaction
AE	Adverse event
ALT	Alanine aminotransferase
ANCOVA	Analysis of covariance

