4.3.6. Pregnancy

Patients will be instructed that if they/their partner become pregnant during the study, the pregnancy should be reported to the investigator. The investigator should also be notified of pregnancy occurring during the study but confirmed after completion of the study. In the event that a patient/patient's partner is subsequently found to be pregnant after the patient is included in the study, then consent will be sought from the partner and, if granted, any pregnancy will be followed and the status of mother and/or child will be reported to the sponsor after delivery. Any patient reporting a pregnancy during the study will be withdrawn from the study.

Men who plan to father a child or to donate sperm within 90 days after last study drug administration (Day 43 or early withdrawal) are not allowed to participate in the study.

Woman who are currently pregnant or nursing, or are planning to conceive a child within 90 days after the last study drug administration (Day 43 or early withdrawal) are not allowed to participate in the study.

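### Do Table 1's 84 capsules and the 3/2/1 blister split leave patients short of study drug or distort compliance?

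*Protocol*

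**What the plan says.** Protocol Section 6 prescribes treatment "once daily for 6 weeks (Table 1"). It adds "Daily dose will consist of 2 capsules containing the intended dose (MIN-117 or Placebo"). Table 1, in the column "During Study Participation", gives 84 capsules for every arm, and 96 as the total dispensed.

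The kit has six blisters, "with each blister containing medication sufficient for 8 days (1 week of treatment and 1 day of overage"). They go out as "Medications blisters will be dispensed to the patients at Visit 2 (3 blisters), Visit 3 (2 blisters), and Visit 4 (1 blister"). Section 6 says this covers daily dosing between visits, including the ±3-day visit windows. Section 13.2 likewise promises enough drug, with overage, for each interval.

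The Time and Events Schedule puts Visits 2, 3, 4 and 5 on Days 1, 15, 29 and 43. Footnote g reads "Only drug administration at Visit 5". Footnote h says of the PK draws at Visits 2 to 5: "Samples will be obtained within 1 hour prior to dosing, and approximately 2 to 4 hours after dosing". Section 4.3.6 refers to the "last study drug administration (Day 43 or early withdrawal").

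Protocol Section 13.5 asks patients to give back all containers, used or not, and forbids re-issuing drug that has come back. It names no visit for the return. Protocol Section 10.4 and SAP Section 3.3.8 define compliance as units taken over units prescribed, where units prescribed are days in the period times units per day.

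**The concern.** Two things look wrong.

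First, Table 1 and the schedule give different numbers of doses. Six weeks at two capsules a day is 84. A patient dosed daily from Day 1 up to and including Day 43 takes 86. If 84 were used as the planned total, a patient who missed nothing would show compliance above 100%.

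Second, the supply is front-loaded. Only one 8-day blister is handed out at Visit 4, yet Visit 5 is nominally 14 days later. If a site read Section 13.5 as requiring everything back at Visits 3 and 4, patients could run out of drug in the last two weeks, before the Week 6 MADRS and the final PK samples. The protocol does not say in so many words that leftover drug stays with the patient.

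**Working it through.** **Table 1 reproduced.** Inputs from Section 6: 6 weeks, 2 capsules a day, 6 blisters of 8 days.

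- Capsules during participation: 6 × 7 × 2 = 84.
- Capsules dispensed: 6 × 8 × 2 = 96.

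Both match Table 1, so the table is consistent with a nominal six weeks.

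**Dose count from the schedule.** Day 1 to Day 43 inclusive is 43 doses, and 43 × 2 = 86 capsules. The Visit 5 dose is intended: Table 2 of Section 8.1.1 lists 9 PK samples, which is 4 visits × 2 draws + 1 at follow-up, so Visit 5 has a pre-dose and a post-dose draw. With the ±3-day window Visit 5 falls on Day 40 to 46:

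| Visit 5 day | Capsules used | Left from 96 |
|---|---|---|
| 40 | 80 | 16 |
| 42 | 84 | 12 |
| 43 | 86 | 10 |
| 46 | 92 | 4 |

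Total supply is sufficient in every permitted case. Actual use equals Table 1's figure when Visit 5 is on Day 42.

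**Compliance.** With 84 as a fixed denominator, full dosing to Day 43 would give 86/84 = 102.4% (80/84 = 95.2% to 92/84 = 109.5% across the window). The written formula does not do this. For a period of Day 1 to Day 43 it prescribes 43 × 2 = 86, so full dosing gives 86/86 = 100%. If the period is taken to end the day before Visit 5, and doses are counted over the same days, it gives 84/84 = 100%.

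**Blister split, remaining drug kept.** Windows: Visit 3 on Day 12–18, Visit 4 on Day 26–32, Visit 5 on Day 40–46, so 7 × 7 × 7 = 343 combinations.

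| Dispensed through | Cumulative days of drug | Latest day to be covered | Spare days |
|---|---|---|---|
| Visit 2 | 24 | 18 (Visit 3) | 6 |
| Visit 3 | 24 + 16 = 40 | 32 (Visit 4) | 8 |
| Visit 4 | 40 + 8 = 48 | 46 (Visit 5 dose included) | 2 |

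Combinations short: 0 of 343. The coverage statement in Section 6 is correct on this reading.

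**Blister split, other collection rules.** These are hypothetical; neither document sets them. Doses on dispensing visits are taken from the new supply.

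- Only unopened blisters kept, blisters used in sequence: on nominal days the patient holds 16 days of drug at Visit 4 against 14 or 15 needed, so is covered. Across the windows, 170 of 343 combinations run short before Visit 5, or 203 counting the Visit 5 dose.
- Everything collected at Visits 3 and 4: the Visit 4–5 shortfall is max(0, V5 − V4 − 8). On nominal days that is 43 − 29 − 8 = 6 days. The range is 0 to 12 days, and it is above zero in 48 of 49 combinations. The Visit 3–4 shortfall, max(0, V4 − V3 − 16), is above zero in 10 of 49, at most 4 days.

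**The case for a change.** The best case for acting is that a protocol should not rely on an unwritten condition. Section 13.2, read interval by interval, promises enough drug for each gap between visits, and one 8-day blister does not fill a 14-day gap. Drug accountability is scheduled at Visits 3, 4 and 5, Section 13.5 wants containers back even when they still hold drug, and returned drug cannot be re-issued to the same patient. A literal-minded site could collect everything at Visit 4. Compliance summaries and monitoring would show the gap only after doses had been missed. One sentence would prevent it.

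It stands that the carry-over is not spelled out, and that 84 and 86 are different counts for the nominal schedule.

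The rest is weaker. Section 13.5 gives no time for the return and bars re-issue only of drug that has been returned; drug the patient keeps has not been returned. Accountability at a visit means counting and does not by itself mean surrender. The 3/2/1 split makes sense only if leftovers are carried forward, and Section 6 states its purpose as covering the windows. A site that collected everything at Visit 4 would be sending a patient home with 8 days of drug for two weeks, which it would see when dispensing. The large shortfall counts describe rules that neither document contains.

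**Conclusion.** No change to the plan follows. The dose-count mismatch is a clerical slip of one nominal day, 84 against 86 capsules, in a descriptive table. Section 6 with Table 1, the schedule with its footnotes, and Section 4.3.6 should be reconciled as an editorial matter; which count is right is for the sponsor to say. Nothing in the analysis depends on it. Supply covers either count, the compliance rule does not cite Table 1, and compliance decides no one's place in an analysis: the ITT and safety populations in SAP Section 4 require only one dose, and SAP Section 6 merely lists non-compliance as a possible deviation.

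The handling of leftover drug at Visits 3 and 4 is missing detail and not a contradiction. Carried forward, as Sections 6, 13.2 and 13.5 together allow, the supply meets all 343 permitted visit combinations with at least 2 days to spare. This assumes that patients keep remaining drug until Visit 5 and that visits stay within ±3 days of their nominal day. The sample size, the Week 6 MADRS comparison and the multiplicity procedure are untouched.

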7. TREATMENT COMPLIANCE

The investigator or designated study center personnel will maintain a log of all study drug dispensed and returned during the study. Study drug supplies for each patient will be inventoried and accounted for throughout the study to verify the patient's compliance with the dosage regimen. Patients will be counseled regarding compliance at every visit.

8. STUDY EVALUATIONS

8.1. Study Procedures

8.1.1. Overview

The [Time and Events Schedule](#) that follows the Synopsis summarizes the frequency and timing of efficacy, PK, PD, and safety measurements applicable to this study.

With the exception of fasting safety laboratory and pre-dose PK blood draws, all visit-specific efficacy assessments during any study visit should be conducted first, before other scheduled tests, procedures, or medical consultations planned for the patients at any specific visit.

A serum pregnancy test is required at Screening, Baseline, and the post-study follow-up visit for all women of childbearing potential. Additional urine pregnancy tests may be performed, as determined necessary by the investigator or required by local regulation, to establish the absence of pregnancy throughout the study.

During the study, including the end-of-study visit, the total blood volume to be collected from each patient will be 136.5 mL (Table 2).

These estimates are for required blood samples and do not include additional blood samples that may be collected at the investigator's discretion for drug level monitoring or other clinical laboratory tests deemed necessary for appropriate patient care in case of occurrence of adverse events.

Table 2: Estimated Blood Volume Drawn

Type of Sample	Volume per Sample (mL)	No. of Samples per Patient	Total Volume of Blood (mL) ^a
Safety			
Hematology	3.5	4	14
Chemistry	5.0	4	20
TSH and Serology ^b	8.5	1	8.5
PK	6	9	54
PD	15	2	30
Pharmacogenomic	10	1	10
Total blood volume drawn			136.5

^a Calculated as number of samples multiplied by amount of blood per sample.

^b Includes HBsAg, anti-HCV, and anti-HIV.

8.1.2. Screening Period (Visit 1)

At the Screening visit, a signed informed consent form for study participation will be obtained. Informed consent must be freely given by the patient and documented by signature before any procedures are performed. The inclusion and exclusion criteria will be reviewed to verify the patient's eligibility, and Screening procedures will be performed as detailed in the Time and Events Schedule.

Patients must meet the DSM-5 diagnostic criteria for moderate to severe MDD, without psychotic features. The diagnosis should be confirmed by using the SCID-5. If patients

give informed consent to participate and meet all study entry criteria at Screening, they will be tapered off their current psychotropic medications. Patients will be free of any psychotropic medications for a period of 1 week or 2 weeks for MAO inhibitors (including reversible inhibitors of monoamine oxidase A), and up to 4 weeks for fluoxetine (i.e., a minimum of 5 half-lives of the drug). This visit may be extended to 4 weeks on a case-by-cases basis after consultation with the sponsor.

8.1.3. Double-Blind Treatment Phase

8.1.3.1. Visits 2 (Baseline Visit /Randomization) 3, 4, and 5/Early Withdrawal (Weeks 1, 2, 4, and 6) – Double-Blind Phase

Patients will undergo 2 consecutive nights of sleep assessments using Somno-Art on the evenings of Day -1, and Day 1. Sleep recording will be done in outpatient settings at select sites. On the morning of Day 1, all inclusion and exclusion criteria will be verified, including all efficacy and safety assessments as per the [Time and Events Schedule](#), and eligible patients will be randomized to 1 of 3 treatment groups: placebo, 5.0 mg MIN-117, or 2.5 mg MIN-117, to receive the first dose of study treatment. Pharmacokinetic blood samples will be drawn within 1 hour before and 2-4 hours after dosing.

Refer to the Time and Events Schedule for evaluations and procedures to be performed during the double-blind treatment phase.

If patients terminate from the study early, they will undergo the Visit 5/Early Withdrawal Visit.

8.1.3.2. Visit 6 (Post-Study Follow-up; Week 8 or 2 Weeks after Early Withdrawal)

At the end of the study, patients will be evaluated for safety/tolerability at the Post-Study Visit, approximately 2 weeks after completing the double-blind treatment phase. Any patient who terminates from the study early will have a Post-Study Follow-up Visit approximately 2 weeks following Early Withdrawal. If any of the laboratory results indicate an abnormality that warrants repeating the test, the patient should be fasting for the repeat assessment. Also, patients with ongoing adverse events at the time of the follow-up visit will be followed until all significant changes have resolved or become medically stable.

8.2. Efficacy

8.2.1. Efficacy Evaluations

Efficacy will be evaluated based on the change from Baseline in the MADRS total score after 6 weeks of treatment or at Early Withdrawal. In addition, other efficacy evaluations will be based on the change from Baseline in the CGI-S, HAM-A total score, A-SEX, DSST score, IDS-SR₃₀, SHAPS, and PSS, and observed CGI-I score. Sleep parameters as assessed by Somno-Art (at select sites) will also be used to evaluate efficacy at specific time points as outlined in the Time and Events Schedule.

Every effort should be made to ensure that all clinician-reported objective measurements are completed by the same individual who made the initial Baseline determinations.

The Montgomery-Asberg Depression Rating Scale (MADRS) – The MADRS is a physician-rated scale designed to measure depression severity and detects changes due to antidepressant treatment. The test consists of 10 items, each of which is scored from 0 (item not present or normal) to 6 (severe or continuous presence of the symptoms), for a total score of 60 ([Attachment 2](#)). Higher scores represent a more severe condition. The MADRS evaluates apparent sadness, reported sadness, inner tension, sleep, appetite, concentration, lassitude, interest level, pessimistic thoughts, and suicidal thoughts. The test exhibits high inter-rater reliability and its capacity to differentiate between responders and non-responders to antidepressant treatment has been shown to be comparable to the Hamilton Rating Scale for Depression.

Hamilton Anxiety Scale (HAM-A) – HAM-A is composed of 14 items, each defined by a series of symptoms ([Attachment 3](#)). The subject is asked to rate the gravity of each item using a 5-level scale – from 0 to 4, where 0 being not present and 4 being severe – and afterwards, the results are collated and tabulated to determine the severity of anxiety.

Clinical Global Impression- Severity and Improvement (CGI-S and CGI-I) – The CGI-S is a physician-rated scale that is designed to rate the severity of the subject's illness at the time of assessment, relative to the clinician's past experience with subjects who have the same diagnosis and improvement with treatment. Considering total clinical experience, a subject is assessed on severity of mental illness at the time of rating according to: normal (not at all ill)=1; borderline mentally ill=2; mildly ill=3; moderately ill=4; markedly ill=5; severely ill=6; or extremely ill=7. The CGI-I is a 7-point scale that requires the clinician to assess how much the subject's illness has improved or worsened relative to a Baseline state at the beginning of the intervention and rated as: 1, very much improved; 2, much improved; 3, minimally improved; 4, no change; 5, minimally worse; 6, much worse; or 7, very much worse.

See [Attachment 4](#) and [Attachment 5](#) for an example of these scales.

Inventory of Depressive Symptoms - Subject-Rated – IDS-SR₃₀ – The 30-item IDS ([Attachment 6](#); [Rush 1996](#)) is designed to assess the severity of depressive symptoms. The IDS is available in the clinician (IDS-C) and self-rated versions (IDS-SR). The IDS assess all the criterion symptom domains designated by the American Psychiatry Association DSM-5 to diagnose a major depressive episode. This assessment can be used to screen for depression, although it has been used predominantly as measures of symptom severity, and is sensitive to change, with medications, psychotherapy, or somatic treatments, making it useful for both research and clinical purposes. The psychometric properties of the IDS have been established in various study samples. The IDS requires minimal training to administer and should be completed in one sitting, and rates symptoms for the prior seven days.

The IDS-SR₃₀ is scored by summing responses to 28 of the 30 items to obtain a total score ranging from 0 to 84. Either appetite increase or decrease, but not both, and weight increase or decrease, but not both, are used to calculate the total score. Higher scores indicate increase in severity of depression.

Snaith-Hamilton Pleasure Scale (SHAPS) – The 14-item SHAPS is a self-administered instrument that is used to measure hedonic capacity (Snaith, 1993). The SHAPS has excellent internal consistency, with construct validity, and is unidimensional in assessing hedonic capacity among adult outpatients with major depressive disorder ([Attachment 7](#)).

The pattern of the SHAPS mean scores is consistent with the scoring direction on the pleasure/enjoyment item of the IDS (Clinician-administered, sub-item 21); that is, those who rarely or are unable to derive pleasure from activities (as coded/scored on IDS sub-item 21) also have higher levels of anhedonia or lower levels of hedonic capacity (as measured via the SHAPS). The SHAPS is not influenced by age, gender, race, education, duration of the current depressive episode, length of illness, or first versus recurrent episode of depression. Each of the items has a set of four response categories--Definitely Agree, Agree, Disagree, and Strongly Disagree, with either of the Disagree responses receiving a score of 1 and either of the Agree responses receiving a score of 0. Thus, the SHAPS is scored as the sum of the 14 items so that total scores ranged from 0 to 14. A higher total SHAPS score indicated higher levels of present state of anhedonia.

Perceived Stress Scale – PSS – The PSS is the most widely used psychological instrument for measuring the perception of stress ([Attachment 8](#)). It is a measure of the degree to which situations in one’s life are appraised as stressful. Items were designed to tap how unpredictable, uncontrollable, and overloaded respondents find their lives. The scale also includes a number of direct queries about current levels of experienced stress. Moreover, the questions are of a general nature and hence are relatively free of content specific to any sub-population group. The questions in the PSS ask about feelings and thoughts during the last month. In each case, respondents are asked how often they felt a certain way ([Cohen 1983](#)).

The Arizona Sexual Experience Scale (A-SEX) – The A-SEX scale is a subject-completed scale designed to measure five specific areas that are the core elements of sexual function ([Attachment 9](#)). The self-reported 5-item scale has male and female specific versions and has been commonly used in clinical studies of depression. The items are answered on 6-point Likert scales, ranging from hyperfunction (1) to hypofunction (6). The recall period is the past week. The total A-SEX score is calculated by adding scores of the five items. Each response option for each item is assigned a score from 1-6 (e.g., 1=extremely strong to 6=none), with the total score ranging on a scale from 5 to 30. Lower scores reflect higher sexual functioning. A total A-SEX score of > 19 indicates sexual dysfunction.

Digit Symbol Substitution Test (DSST) – The DSST will be used to evaluate cognition. The DSST is a neuropsychological test sensitive to brain damage, dementia, age, and depression. It consists of digit-symbol pairs (e.g., 1/-, 2/⊥ ... 7/Λ, 8/X, 9/=) followed by a list of digits. Under each digit the subject should write down the corresponding symbol as fast as possible. The number of correct symbols within the allowed time (e.g., 90 or 120 sec) is measured.

See [Attachment 10](#) for an example of this test.

Somno-Art – Somno-Art is a new methodology to score sleep. The device is worn on the non-dominant forearm and records the cardiac cycle by photoplethysmography, while body movements are recorded by the integrated actimetry. The actimetry is measured through the vector magnitude of accelerations obtained every second in the three dimensions of the space

The cardiac and actimetry data are sampled and stored at 1 Hz. The data are then post-processed in 1-second average “.srt” files that are used for sleep analysis using the Somno-Art methodology.

The following sleep parameters will then be extracted:

Sleep Onset Latency (SOL): elapsed time between light out time and the first occurrence of any sleep stage other than stage W.

REM sleep Latency (REML): elapsed time between sleep onset and the first occurrence of REM sleep.

Wake After Sleep Onset (WASO): cumulative time of wake episodes occurring between sleep onset and light on time.

Time spent in each sleep stage: cumulative time spent in each sleep stages (N1, N2, N3 or REM sleep) between sleep onset and light on time.

Total Sleep Time (TST): cumulative time spent in N1, N2, N3 and REM sleep from sleep onset to light on time.

Sleep Efficiency Index (SEI): ratio between total sleep time divided by time in bed.

Number of awakenings (NAW): number of wake episodes exceeding 15 seconds, between sleep onset and light on time.

Number of Sleep Cycles (NSC): a sleep cycle was defined as the elapsed time between sleep onset and the end of the first REM sleep phase (1st cycle) or the end of one REM sleep phase to the end of the following REM sleep phase (2nd and following cycles). A REM sleep phase can be constituted by several REM sleep episodes. Two successive REM sleep episodes were considered as parts of the same REM sleep phase when they were separated by less than 20 min of any other sleep stage.

